7.5.1 Analysis of Progression-Free Survival

The primary objective of the study is to compare the PFS per BICR of Arm A to Arm C in randomized subjects with previously untreated (first line) advanced or metastatic RCC. All the analyses outlined in this section are specified for the all randomized subjects population in Arm A and Arm C, unless otherwise specified.

PFS per BICR will be compared between the treatment groups via stratified log-rank test among all randomized subjects at a two-sided $\alpha = 0.05$ level. The stratification factors will be IMDC prognostic risk score (0 vs 1-2 vs 3-6), region (US/Canada/W Europe/N Europe vs ROW) and PD-L1 status ($\geq 1\%$ vs $< 1\%$ or indeterminate).

The primary definition of PFS adjusting for subsequent anticancer therapy will be used in this analysis. The two-sided log-rank p-value will be reported.

The estimate of the PFS hazard ratio between treatment groups will be calculated using a stratified Cox proportional hazards model, with treatment as the sole covariate. Ties will be handled using the exact method. A two-sided 95% CI for the hazard ratio will also be presented.

The PFS function for each treatment group will be estimated using the KM product limit method and will be displayed graphically. A two-sided 95% CI for median PFS in each treatment group will be computed via the log-log transformation method. PFS rates at fixed time points (e.g. 6 months, depending on the minimum follow-up) will be presented along with their associated 95% CIs. These estimates will be derived from the Kaplan Meier estimate and corresponding CIs will be derived based on Greenwood¹¹ formula for variance derivation and on log-log transformation applied on the survivor function¹².

Analyses of PFS will also be conducted based on the secondary definition of PFS. These analyses will be the same as those specified above.

The source of PFS event (progression or death) will be summarized by treatment group. The status of subjects who are censored (as per primary definition of PFS) in the PFS KM analysis will be tabulated for each treatment group including the following categories:

- On-study (on-treatment, in follow-up)
- Off-study (lost to follow-up, withdraw consent, never treated)
- No baseline tumor assessment
- No on-study tumor assessment and no death
- Received subsequent anticancer therapy

A by-subject listing will be presented including treatment group, PFS duration under the primary definition, PFS duration on the ITT definition, whether the subject was censored under the primary definition, and if censored, the reason, and whether the subject was censored under the ITT definition, and if censored, the reason.

A by-subject listing of lesion evaluations per BICR will be presented.

Note that similar tables (KM plot, median PFS with its 95% CI, PFS rates, source of PFS event, and status of subjects who are censored) along with by-subject listing will be summarized for all intermediate/poor risk subjects in Arm A and Arm C.

For those subjects who randomized to Arm B prior to Revised Protocol 01, the PFS function will be estimated using the KM product limit method and reported separately for Arm B. A two-sided

95% CI for median PFS will be computed via the log-log transformation method. A by-subject listing will be presented including treatment group, PFS duration under the primary definition, PFS duration on the ITT definition, whether the subject was censored under the primary definition, and if censored, the reason, and whether the subject was censored under the ITT definition, and if censored, the reason.

7.5.2 Supportive Analyses of Progression-Free Survival

The following sensitivity analyses will be conducted using both the primary and the secondary definition of PFS in all randomized subjects:

- 1) Delayed effect of immunotherapy interventions may cause a late separation in the PFS KM curves and non-proportional hazards. PFS (as determined by BICR) will be compared between treatment groups via two-sided 0.05 stratified weighted log-rank test among subjects. The primary definition of PFS will be used in this analysis. The two-sided stratified weighted log-rank p-value will be reported using G ($\rho = 0$, $\gamma = 1$) weights, in the terminology of Fleming and Harrington¹³.
 - a) The Fleming Harrington test can be unstable, so it is possible, though uncommon, that the p-value for this trial will not be estimable.
 - b) The estimate of the PFS hazard ratio in the period before and following 6 months will be calculated using a stratified time-dependent Cox model with effects for treatment and period-by-treatment interaction. In this model, period is a binary variable indicating pre- vs. post-6 months. Ties will be handled using the exact method. A two-sided 95% CI for the hazard ratio will also be presented.
- 2) A multivariate Cox regression model will be used in order to estimate the treatment effect after adjustment for possible imbalances in known or potential prognostic factors. The factors used in the randomization, which, by definition, will be balanced across treatment groups, will still be included in the model as stratification factors. However, all additional factors will be incorporated as covariates. The additional factors, which are all measured at baseline, will include:
 - a) Age categorization (< 65 vs. ≥ 65)
 - b) Gender (Male vs. Female)
 - c) Race
 - d) Region (US/Canada/W.Europe/N.Europe vs. ROW)
 - e) IMDC score (0 vs 1-2 vs 3-6)
 - f) Karnofsky performance status (100-90, <90)
 - g) Prior Nephrectomy (Yes, No)
 - h) LDH level ($\leq 1.5 \times \text{ULN}$, $> 1.5 \times \text{ULN}$)
 - i) Baseline PD-L1+ status based on a 1% cut off
 - j) Number of organ with metastasis (1 vs. ≥ 2)

The level of the covariate normally associated with the worst prognosis will be coded as the reference level. The hazard ratio associated with treatment and with each of the baseline covariates will be presented along with associated 95% CIs.

3) PFS using stratification factors as obtained from the baseline CRF pages (instead of IRT). The hazard ratio associated with treatment will be presented along with the associated two-sided 95% CIs. This analysis will be performed only if at least one stratification variable/factor at randomization (as per IRT) and baseline are not concordant for at least 10% of the randomized subjects.

4) PFS using the investigator's assessment. The hazard ratio associated with treatment and median PFS will be presented along with the associated two-sided 95% CIs.

A cross tabulation of PFS assessment by BICR versus PFS assessment by investigator will be presented, by treatment group. Concordance Rate of event will be computed as the frequency with which investigator and BICR agree on classification of a subject as event versus censored as a proportion of the total number of randomized subjects assessed by both the investigator and BICR.

A by-subject listing of PFS assessment per BICR and investigator will be presented.

5) PFS using an un-stratified log rank test. The hazard ratio associated with treatment will be presented along with the associated two-sided 95% CIs.

6) PFS using an un-stratified Cox proportional hazards model, adjusted, using as covariates only the stratification factors used in randomization. The hazard ratio associated with treatment will be presented along with the associated two-sided 95% CIs.

7) PFS for subjects with no relevant protocol deviations. This analysis will be conducted only if there are more than 10% subjects with relevant protocol deviations. The hazard ratio associated with treatment will be presented along with the associated two-sided 95% CIs.

[figure not shown]
8) The method of Gail and Simon¹⁴ will be used to test for a qualitative interaction between treatment and strata. This test will be conducted at $\alpha=0.10$ level. The p-value reported from this specific analysis is for descriptive purposes alone.

9) To examine the assumption of proportional hazards in the Cox regression model, in addition to treatment, a time-dependent variable defined by treatment by time interaction will be added into the model. A two-sided Wald Chi-square p-value of less than 0.1 may indicate a potential nonconstant treatment effect. [REDACTED].

10) PFS using censoring for 2 missing TA

[REDACTED]

[REDACTED]

[Redacted text block]

7.5.4 Analysis of Overall Survival

One of the secondary objectives of the study is to compare the overall survival of Arm A to Arm C in all randomized subjects. All the analyses outlined in this section are specified for the all randomized subjects population in Arm A and Arm C, unless otherwise specified.

If the formal analysis of PFS among all randomized subjects is statistically significant, the formal interim analysis of OS among all randomized subjects will be tested, as per hierarchical testing procedure.

Overall survival will be compared between the treatment groups at the interim and final analyses, using stratified log-rank test. The stratification factors will be those used in the analysis of PFS. An O'Brien and Fleming α -spending function will be employed to determine the nominal significance levels for the interim and final analyses. The stratified hazard ratio between the treatment groups will be presented along with $100*(1-\alpha)\%$ CI (adjusted for interim). In addition, two-sided p-value will also be reported for the analysis of OS.

OS will be estimated using the KM techniques. A two-sided 95% CI for median OS in each treatment group will be computed via the log-log transformation method. OS rates at fixed time points (e.g. 6 months, depending on the minimum follow-up) will be presented along with their associated 95% CIs. These estimates will be derived from the Kaplan Meier estimate and corresponding CIs will be derived based on Greenwood formula for variance derivation and on log-log transformation applied on the survivor function.

The status of subjects who are censored in the OS KM analysis will be tabulated for each treatment group using the following categories:

- On-study (on-treatment, in follow-up)
- Off-study (lost to follow-up, withdraw consent, never treated)

A by-subject listing will be presented including treatment group, first and last dose date, whether the subject died, and if censored, the reason, event/censored date and OS duration.

Note that similar tables (KM plot, median OS with its 95% CI, OS rates, and status of subjects who are censored) along with by-subject listing will be summarized for all intermediate/poor risk subjects in Arm A and Arm C.

The analysis performed for PFS (detailed in [section 7.5.8](#)) for those subjects who randomized to Arm B prior to Revised Protocol 01 will be repeated for OS.

[REDACTED]

7.5.6 Current Status of PFS and OS Follow-up

The extent of follow-up for survival, defined as the time between randomization date and last known alive date (for subjects who are alive) or death date (for subjects who died), will be summarized descriptively (median, min, max, etc.) in months for all randomized subjects.

The currentness of follow-up for survival, defined as the time between last OS contact (i.e., last known alive date or death date) and cutoff date (defined by last subject last visit date), will be summarized in months for all randomized subjects. Subjects who died and subjects with last known alive date on or after data cut-off date will have zero value for currentness of follow-up.

Minimum follow-up of OS for all randomized subjects, defined as the time from cutoff date to last subject's randomization date, will be summarized in months.

Time from last evaluable tumor assessment to cutoff date in months will be summarized by treatment group and overall for all randomized subjects. Subjects who have a PFS event will be considered as current for this analysis. The secondary definition of PFS will be used for this summary.

In addition, time to treatment discontinuation will be summarized and presented by treatment group using a Kaplan-Meier curve whereby the last dose date will be the event date for those subjects who are off study therapy. Median duration of study therapy and associated 95% CI will be provided. Subjects who are still on study therapy will be censored on their last dose date.

A by-subject listing will also be produced to accompany the subject time from last evaluable tumor assessment.

7.5.7 Interim Analysis of Overall Survival

An independent statistician external to BMS will perform the analysis. In addition to the formal planned interim analyses for OS, the Data Monitoring Committee (DMC) will have access to periodic un-blinded interim reports of efficacy and safety to allow a risk/benefit assessment. Details are included in the DMC charter.

Two interim analyses of OS are planned for this study. The first interim analysis of OS is planned at the time of final PFS analysis and expected after observing 165 deaths (approximately 65% of the targeted OS events) have been observed among all randomized subjects in Arm A and Arm C based on above accrual rate and the exponential distribution in each arm. These formal comparisons of OS will allow for early stopping for superiority, and the boundaries for declaring superiority will be derived based on the actual number of deaths using Lan-DeMets spending function with O'Brien and Fleming type of boundary in EAST version 6. If the first interim analysis is performed exactly at 165 deaths, the boundary in terms of statistical significance for declaring superiority would be 0.011 (HR=0.673 with 16 months improvement in median OS for the Arm A versus Arm C comparison (33 versus 49 months)). The second interim analysis of OS is expected after observing 211 deaths (approximately 83% of the targeted OS events) have been observed among all randomized subjects based on above accrual rate and the exponential distribution in each arm. The boundary for declaring superiority in terms of statistical significance for the second interim analysis after 211 events would be 0.025 (HR=0.734 with 12 months improvement in median OS for the doublet versus sunitinib comparison (33 versus 45 months)). The boundary for declaring superiority in terms of statistical significance for the final analysis after 254 events would be 0.041 (HR=0.774 with 9.6 months improvement in median OS for the Arm A versus Arm C comparison (33 versus 42.6 months)).

Note that if the analysis of PFS final analysis and first interim analysis OS is trigger with 8-months minimum follow-up on all randomized subjects, minimum 283 PFS events and 149 OS events, then the details of the first interim analysis of OS will be as follows:

- If the first interim analysis is performed exactly at 149 deaths, the boundary in terms of statistical significance for declaring superiority would be 0.007 (HR=0.643 with 18.3 months improvement in median OS for the Arm A versus Arm C comparison (33 versus 51.3 months)).

The DMC will review the safety and efficacy data from the informal interim analyses, BMS will remain blinded to these interim results and will determine if the study should continue with or without changes or if accrual should be stopped. Subject enrollment will continue while waiting for the DMC's decisions.

The chair of the DMC and the sponsor can call an unscheduled review of the safety data.

If the formal analysis of PFS among all randomized subjects is statistically significant, the formal interim analysis of OS among all randomized subjects will be tested, as per hierarchical testing procedure.

At the time of the formal interim analysis for superiority of OS, the DMC may recommend continuing or stopping the trial. If the trial continues beyond the formal interim analysis, BMS will remain blinded to these interim results and the nominal critical point for the final OS analysis will be determined using the recalculated information fraction at the time of the interim analysis, as described above. The final OS hazard ratio and corresponding confidence interval will be reported whereby the confidence interval will be adjusted accordingly (i.e. using the recalculated nominal α level at the final analysis).

If the trial is stopped for superiority of OS at the interim, the p-value from the interim stratified log-rank test will be considered the final primary analysis result.

7.5.8 Analysis of Objective Response Rate

One of the secondary objectives of the study is to evaluate the objective response rate in all randomized subjects in Arm A and Arm C. All the analyses outlined in this section are specified for the all randomized subjects population in Arm A and Arm C, unless otherwise specified. If the formal analysis of OS among all randomized subjects is statistically significant, the formal analysis of ORR among all randomized subjects will be tested, as per hierarchical testing procedure. Note that the formal ORR analysis specified in the SAP supersede those specified in the protocol.

The number and percentage of subjects in each category of BOR per BICR (complete response [CR], partial response [PR], stable disease [SD], progressive disease [PD], or unable to determine [UTD]) will be presented, by treatment group. Estimates of response rate, along with its exact two-sided 95% CI by Clopper and Pearson¹⁵ will be presented, by treatment group.

Similar analyses will be repeated based on the investigator's assessment of ORR. A cross tabulation of BICR best response versus the investigator best response will be presented, by treatment group and by response categories. Concordance Rate of Responders will be computed as the frequency with which investigator and BICR agree on classification of a subject as responder vs. non responder/UTD as a proportion of the total number of randomized subjects assessed by both the investigator and BICR.

The following subject-level graphics will also be provided:

- For the responders only, time courses of the following events of interest will be graphically displayed: tumor response, progression, last dose received, and death.

- For response evaluable subjects (randomized subjects with baseline and at least one on-study tumor assessment),
 - A bar plot showing the best % reduction from baseline in sum of diameter of target lesions based on BICR assessment for each subject will be produced (excluding assessments after PD and assessments after start of subsequent anti-cancer therapy).
 - A plot of individual time course of tumor burden change per BICR assessment will be produced.

A by-subject listing of best overall response will be presented including treatment group, best overall response per BICR and dates of CR/PR/progression.

A by-subject listing of per time point tumor response per BICR will be presented.

Note that similar tables along with by-subject listing will be summarized for all intermediate/poor risk subjects in Arm A and Arm C.

For those subjects who randomized to Arm B prior to Revised Protocol 01, estimates of response rate, along with its exact two-sided 95% CI by Clopper-Pearson method, will be computed per BICR and investigator. DOR and TTR will also be evaluated per BICR.

7.5.10 Time to Tumor Response and Duration of Response

The analyses specified in this section will be conducted for all treatment arms. Duration of response (DOR) and time to response (TTR) will also be evaluated for subjects who achieved confirmed PR or CR. The DOR for each treatment group will be estimated using the Kaplan-Meier (KM) product limit method and will be displayed graphically. A table will be produced presenting number of events, number of subjects involved, medians, and 95% CIs for the medians. Median values of DOR, along with two-sided 95% CI in each treatment group will be computed based on a log-log transformation method.

The status of subjects who are censored in the DOR KM analysis will be tabulated for each treatment group including the following categories:

- Ongoing follow-up (current [last scan within adequate window vs cutoff date], not current)
- Off-study (lost to follow-up, withdraw consent, never treated)
- Received subsequent anticancer therapy.

TTR, which does not involve censoring, will be summarized by treatment group in all responders using descriptive statistics.

Cumulative Response Rates will be tabulated for Week 8, Month 4, 6, 8, and 12, and overall response rate will be provided.

A by-subject listing will be presented including treatment group, best response, time to response, duration of response, whether the subject was censored for duration of response, and, if so, the reason.

[REDACTED]

7.6 Safety

Analyses in this section will be tabulated for all treated subjects by treatment group as treated, unless otherwise specified.

Analyses in this section will be tabulated for all treated subjects in Arm A and Arm C, unless otherwise specified. Limited selection of the summary tables will be generated for those subjects who randomized to Arm B prior to Revised Protocol 01, which is specified in the relevant subsections below.

7.6.1 Deaths

Deaths will be summarized by treatment group:

- All deaths, reasons for death.
- Deaths within 30 days of last dose received, reasons for death.
- Deaths within 100 days of last dose received, reasons for death.

A by-subject listing of deaths will be provided for the all enrolled subjects population.

Note that for all intermediate/poor risk treated subjects in Arm A and Arm C, deaths will be summarized by treatment group.

Similar tables will be presented for those subjects treated in Arm B.

7.6.2 Serious Adverse Events

Serious adverse events will be summarized by treatment group:

- Overall summary of SAEs by worst CTC grade (any grade, grade 3-4, grade 5) presented by SOC/PT.
- Overall summary of drug-related SAEs by worst CTC grade (any grade, grade 3-4, grade 5) presented by SOC/PT.

All analyses will be conducted using the 30-day safety window.

A by-subject SAE listing will be provided for the “enrolled subjects” population.

Note that for all intermediate/poor risk treated subjects in Arm A and Arm C, serious adverse events will be summarized by treatment group.

Similar tables will be presented for those subjects treated in Arm B.

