5 SAMPLE SIZE AND POWER

The sample size calculations of this study summarized below are based on the target randomized subjects in Arm A and Arm C only. That is, the total randomized subjects will be higher than the target randomized subjects due to randomized subjects into Arm B prior to implementation of CA2099ER Global Revised Protocol 01, which stopped further randomization into Arm B.

The sample size of this study accounts for the primary endpoint of progression-free survival (PFS) per BICR in all randomized subjects. Assuming a 25% screen failure rate, it is expected that approximately 850 subjects will need to be enrolled in order to randomize 638 subjects (319 per arm) in a 1:1 ratio. To represent the normal frequency of the favorable risk group in mRCC, the favorable risk subjects are capped at approximate 25%; thus, at most 212 favorable risk subjects (106 per arm) will be enrolled to randomize 160 favorable risk subjects in a 1:1 ratio. The rest of the enrolled participants will provide approximately 478 intermediate/poor risk randomized subjects (239 per each arm).

The overall alpha for this study is 0.05 (two-sided). PFS will be evaluated for treatment effect at an alpha of 0.05 (two-sided), with at least 95% power. No interim analysis of PFS is planned. OS will be evaluated for treatment effect at an alpha level of 0.05 (two-sided) with 80% power, accounting for two formal interim analyses to assess efficacy.

Sample Size Justification for Primary PFS Endpoint

The primary endpoint of PFS per BICR of Arm A versus Arm C analysis conducted on all randomized subjects. The PFS analysis will occur after approximately 9-10 months minimum

follow-up on all randomized subjects, which will be triggered by approximately 350 events from Arm A and Arm C. The 350 PFS events provide at least 95% power to detect a HR of 0.68 for PFS of Arm A versus Arm C with a type I error of 0.05 (two-sided). The HR of 0.68 corresponds to a 47% increase in the median PFS, assuming a median PFS of 18.2 months for Arm A and 12.4 months for Arm C. It is projected that an observed HR of 0.811 or less, which corresponds to a 2.89 month or greater improvement in median PFS (12.4 versus 15.3 months), would result in a statistically significant improvement in PFS for the Arm A versus Arm C comparison.

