6 STUDY PERIODS, TREATMENT REGIMENS AND POPULATIONS FOR ANALYSES

6.1 Study Periods

- Baseline period:
 - Baseline evaluations or events will be defined as evaluations or events that occur before the date and time of the first dose of study treatment. Evaluations (laboratory tests, pulse oximetry and vital signs) on the same date and time of the first dose of study treatment will be considered as baseline evaluations. Events (AEs) on the same date and time of the first dose of study treatment will not be considered as pre-treatment events.
 - In cases where the time (onset time of event or evaluation time and dosing time) is missing or not collected, the following definitions will apply:
 - ◆ Pre-treatment AEs will be defined as AEs with an onset date prior to but not including the day of the first dose of study treatment;
 - ◆ Baseline evaluations (laboratory tests, pulse oximetry and vital signs) will be defined as evaluations with a date on or prior to the day of first dose of study treatment.
 - If there are multiple valid assessments on or prior to the first dose of study treatment:
 - ◆ For laboratory tests, the latest non missing labs value on or before first dose date (and time if collected) will be used as the baseline in the analyses. For 'LIPASE' and 'GLUCOSE', for treated subjects only, the last predose assessment with non-missing toxicity grade will be considered as baseline. If multiple assessments exist with the same collection date (and time if collected) and entry date and time, then the first observation is used as baseline.

- Post baseline period:
 - On-treatment AEs will be defined as AEs with an onset date and time on or after the date and time of the first dose of study treatment (or with an onset date on or after the day of first dose of study treatment if time is not collected or is missing). For subjects who are off study treatment, AEs will be included if event occurred within a safety window of 30 days (or 100 days depending on the analysis) after the last dose of study treatment. No “subtracting rule” will be applied when an AE occurs both pre-treatment and post-treatment with the same preferred term and grade.

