7.6.3 Adverse Events Leading to Discontinuation of Study Therapy

AEs leading to discontinuation will be summarized by treatment group:

- Overall summary of AEs leading to discontinuation by worst CTC grade (any grade, grade 3-4, grade 5) presented by SOC/PT.
- Overall summary of drug-related AEs leading to discontinuation by worst CTC grade (any grade, grade 3-4, grade 5) presented by SOC/PT.

The analyses will be conducted using the 30-day safety window.

A by-subject AEs leading to discontinuation listing will be provided.

Note that for all intermediate/poor risk treated subjects in Arm A and Arm C, AEs leading to discontinuation will be summarized by treatment group.

Similar table will be presented for those subjects treated in Arm B.

Note that

- for Arm A, AEs leading to discontinuation from cabozantinib only, nivolumab only, and both cabozantinib and nivolumab.
- for Arm B, AEs leading to discontinuation from cabozantinib only, nivolumab and ipilimumab only, and from cabozantinib, nivolumab, and ipilimumab will be summarized in all the tables specified in this section.

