7.6.9 Multiple Events

The following summary tables will be provided:

- A table showing the total number and rate (exposure adjusted) of occurrences for all AEs.
- A table showing the total number and rate (exposure adjusted) of occurrences for AEs occurring in at least 5% of subjects in any treatment group.

In addition, the rate (exposure adjusted) and its 95% CI evaluated for different time intervals will be displayed graphically for each treatment group. This analysis will be limited to the rate of all AEs and all drug-related AEs. The analyses will be conducted using the 30-day safety window.

A listing displaying the unique instances of all AEs, i.e., after duplicates have been eliminated and overlapping and contiguous occurrences of the same event (i.e. same PT) have been collapsed will be provided. No formal comparisons will be made between treatment groups.

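### Serious, grade 3-4 and discontinuation adverse events are summarised only as crude percentages over windows that the design expects to be longer in Arm A; adding first-event exposure-adjusted rates would be a cheap improvement

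*SAP*

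**What the plan says.** For serious adverse events, SAP 7.6.2 asks for an "Overall summary of SAEs by worst CTC grade (any grade, grade 3-4, grade 5) presented by SOC/PT" and adds that "All analyses will be conducted using the 30-day safety window". For discontinuations, SAP 7.6.3 asks for an "Overall summary of AEs leading to discontinuation by worst CTC grade (any grade, grade 3-4, grade 5) presented by SOC/PT", also on the 30-day window. SAP 7.6.5 tabulates adverse events by worst grade on the 30-day window. Only the drug-related summary by any grade, grade 3-4 and grade 5 is repeated at 100 days, and that window also runs from last dose.

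The summary measure is the number and proportion of subjects (SAP 7.1), each counted once per term (SAP 7.1.1). SAP 6.1 ties the end of the window to last dose: for subjects off treatment, "AEs will be included if event occurred within a safety window of 30 days", or 100 days for some analyses.

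Cabozantinib in Arm A and sunitinib in Arm C both continue to progression or unacceptable toxicity (SAP 2). The 2-year limit applies to nivolumab only. SAP 5 sizes the trial "assuming a median PFS of 18.2 months for Arm A and 12.4 months for Arm C".

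SAP 7.1.1 and 7.6.9 do plan rates per 100 person-years. They cover occurrences of all adverse events, occurrences of events seen in at least 5% of subjects, and a plot by time interval. Of the plot the SAP says: "This analysis will be limited to the rate of all AEs and all drug-related AEs".

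**The concern.** A once-per-subject percentage grows with the length of time over which events are counted. Here that time is set by treatment duration, and the trial's own hypothesis is that progression, and hence the end of treatment, comes later in Arm A. If the hypothesis is right, the two columns of each table describe unequal observation time.

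Serious, grade 3-4 and discontinuation events weigh heavily in a benefit-risk reading. They are also the categories for which SAP 7.6.9 gives no separate rate; its tables count repeated occurrences at any grade. Time to onset of select adverse events (SAP 7.6.6.2) does not fill the gap, because it is restricted to subjects who had the event. A reader who sees a few points more in Arm A could not tell from these tables whether the regimen is more toxic per month of treatment or was simply given for longer.

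**Working it through.** **Inputs from the documents.** Accrual of 3 per month for 4 months, then 42 per month, over 19 months; 319 per arm; median PFS 18.2 and 12.4 months; primary analysis at month 29 (SAP 5). Safety is analysed at the primary analysis (Protocol 10.3.2). The window ends 30 days after last dose, which is W = 30/30.4375 = 0.986 months.

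**Assumptions not in the documents.** Treatment ends at progression; PFS is exponential; the first-event hazard h is the same in both arms. The values of h are illustrative.

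**1. The plan's own figures reproduce.**
- Power with 350 events at HR 0.68 is Φ(½·√350·|ln 0.68| − 1.96) = Φ(3.608 − 1.960) = 0.950.
- The critical HR is exp(−2 × 1.96/√350) = 0.811.
- With the stated accrual and medians, the expected event fractions at month 29 are 0.4825 and 0.6160. Then 319 × 0.4825 + 319 × 0.6160 = 350.4 events.

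**2. Mean window at month 29.** Let λ = ln 2/median, giving 0.0381 (A) and 0.0559 (C), and let F be a participant's time from randomization to cutoff. The window is min(T + W, F). Its mean, averaged over accrual, is W + (1 − exp(−λ(F − W)))/λ. This gives 13.1 months in Arm A and 11.6 in Arm C, a ratio of 1.13. The ratio of treatment times reaches 18.2/12.4 = 1.47 only with complete follow-up; the administrative cutoff removes most of the difference.

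**3. Crude percentage under equal constant hazard.** The crude percentage is the average of 1 − exp(−h × window). The SE is √[pA(1−pA)/319 + pC(1−pC)/319].

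| h per month | Arm A | Arm C | Difference | SE |
|---|---|---|---|---|
| 0.02 | 22.5% | 20.1% | 2.4 | 3.2 |
| 0.04 | 38.9% | 35.1% | 3.8 | 3.8 |
| 0.06 | 51.1% | 46.5% | 4.6 | 4.0 |

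A discontinuation event itself ends treatment, so its crude percentage is the average of h/(h+λ) × (1 − exp(−(h+λ)F)). With a 1-year risk of 10% this is 10.4% vs 9.1%; with 20% it is 20.4% vs 17.9%.

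**4. Sensitivity to hazard shape and dropout.**
- All hazard in the first 3 months, with 3-month risk of 10% to 50%: the difference is 0.1 to 0.5 points.
- Hazard tripled in the first 3 months over a base of 0.02 or 0.04: 2.2 to 3.2 points.
- Constant hazard plus other discontinuation at an equal rate in both arms (median 12 to 48 months), with 1-year event risks of 20% to 60%: 1.3 to 4.3 points.

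**5. What the added measures would show under equal constant hazard.**
- First-event rate: expected person-time to first event or window end is crude/h. At h = 0.04 that is 0.3891/0.04 = 9.73 months in Arm A and 0.3511/0.04 = 8.78 in Arm C. Events over person-time is then 0.04 in both arms, a ratio of 1.00.
- Twelve-month risk with window end as censoring: 1 − exp(−12h), equal in both arms (21.3%, 38.1% and 51.3%).
- Twelve-month risk with window end as a competing event: 17.9 vs 16.6%, 32.3 vs 30.0% and 43.8 vs 40.9%. A gap of 1.3 to 2.9 points remains.

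**The case against.** The strongest reply is that the crude percentage is a legitimate quantity. Under a treat-to-progression regimen, longer exposure is part of the strategy, and the share of patients who ever have a serious event is worth reporting. That stands, and is why the crude tables should stay. It does not answer the separate question of toxicity per unit of exposure.

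The plan also does not ignore exposure. Besides the rates in SAP 7.6.9, it summarises duration of therapy by arm (SAP 7.4.1) and gives a Kaplan-Meier curve for time to treatment discontinuation (SAP 7.5.6). A reader will see that exposure differs, but will have no rate for the three categories.

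The exposure model is approximate. Treatment decisions follow the investigator's assessment, not the BICR assessment (Protocol 9.1.2). Treatment beyond progression is permitted (Protocol 8.1.4), and toxicity also ends treatment. These could move the exposure ratio either way.

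A reader might infer that equal toxicity must show as excess harm in Arm A. The documents give no hazard shape, and with early events the gap nearly vanishes. A reader might also infer a gap that widens at later database locks; at month 40 the constant-hazard calculation gives 4 to 7 points. But the protocol places the safety analysis at the primary endpoint analysis, and no later safety comparison is specified. Finally, no between-arm inference is at risk: Protocol 10.3.2 makes safety descriptive, and SAP 7.6.9 rules out formal comparisons for its tables.

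**Conclusion.** The point holds as a gap in descriptive reporting. Serious, grade 3-4 and discontinuation events are reported by arm only as crude proportions over windows tied to last dose, with no exposure-adjusted counterpart specified, while the design implies longer observation in Arm A (mean 13.1 vs 11.6 months at month 29).

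Under equal constant hazards of 0.02 to 0.06 per month, the resulting crude excess is about 2 to 5 points, roughly one standard error of the difference. It is 0.1 to 0.5 points if all events fall in the first 3 months. Both ranges rest on treatment ending at progression and on assumed hazards. The crude tables are not wrong, and no test or error rate is affected. The change is worth making because it is cheap and helps separate longer exposure from higher toxicity.

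**What to change.** In SAP 7.6.9, add by arm the exposure-adjusted incidence rate of the first event, with 95% CI, for serious events, drug-related serious events, grade 3-5 events and events leading to discontinuation. Person-time should stop at the first event or at window end, whichever comes first.

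Also add time-to-first-event estimates at 6 and 12 months, with window end treated as censoring and the result labelled as risk while on treatment. If a competing-event version is shown, label it as absolute risk that still depends on treatment duration. The two should not be offered as interchangeable.

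Keep the crude tables, and state that they are to be read together with these rates and the planned duration-of-therapy summaries.

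The cost is SAP wording and a few tables. The event dates are already collected, and the person-time derivation in SAP 7.1.1 needs only a first-event variant. Trial conduct, alpha and sample size do not change. One limitation is that a constant-rate summary is imperfect when the hazard changes over time, which the 6- and 12-month estimates partly address. Another is that the censored estimates assume window end is unrelated to the risk of the event.
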